## 8.3 Endpoints

### 8.3.1 Primary Endpoint(s)

No primary endpoints are defined for this protocol.

### 8.3.2 Secondary Endpoint(s)

No secondary endpoints are defined for this protocol.

## 8.4 Analyses

### 8.4.1 Demographics and Baseline Characteristics

Summary statistics of all demographics and baseline characteristics will be provided by treatment group using the as-treated analysis population.

#### **8.4.3 Safety Analyses**

The evaluation of drug safety is primarily based on clinical adverse events and laboratory abnormalities reported during the study.

Frequency distributions and listings of all adverse events, deaths, serious adverse events, events leading to discontinuation and adverse events of special interest will be generated. Adverse events of special interest are infections, malignancies, autoimmune disorders and injection site reactions.

Laboratory marked abnormalities, using pre-defined abnormality criteria, will also be descriptively summarized.

#### **8.4.4 Pharmacokinetic Analyses**

Not Applicable.

#### **8.4.6 Outcomes Research Analyses**

Not applicable

#### **8.4.7 Other Analyses**

Not applicable

### **8.5 Interim Analyses**

Not applicable

## **9 STUDY MANAGEMENT**

### **9.1 Compliance**

#### **9.1.1 *Compliance with the Protocol and Protocol Revisions***

The study shall be conducted as described in this approved protocol. All revisions to the protocol must be discussed with, and be prepared by, BMS. The investigator should not implement any deviation or change to the protocol without prior review and documented approval/favorable opinion from the IRB/IEC of an amendment, except where necessary to eliminate an immediate hazard(s) to study subjects.

If a deviation or change to a protocol is implemented to eliminate an immediate hazard(s) prior to obtaining IRB/IEC approval/favorable opinion, as soon as possible the deviation or change will be submitted to:

- IRB/IEC for review and approval/favorable opinion
- BMS
- Regulatory Authority(ies), if required by local regulations

Documentation of approval signed by the chairperson or designee of the IRB(s)/IEC(s) must be sent to BMS.

If an amendment substantially alters the study design or increases the potential risk to the subject: (1) the consent form must be revised and submitted to the IRB(s)/IEC(s) for review and approval/favorable opinion; (2) the revised form must be used to obtain consent from subjects currently enrolled in the study if they are affected by the amendment; and (3) the new form must be used to obtain consent from new subjects prior to enrollment.

If the revision is done via an administrative letter, investigators must inform their IRB(s)/IEC(s).

#### **9.1.2 *Monitoring***

BMS representatives will review data centrally to identify potential issues to determine a schedule of on-site visits for targeted review of study records.

Representatives of BMS must be allowed to visit all study site locations periodically to assess the data quality and study integrity. On site they will review study records and directly compare them with source documents, discuss the conduct of the study with the investigator, and verify that the facilities remain acceptable.

In addition, the study may be evaluated by BMS internal auditors and government inspectors who must be allowed access to CRFs, source documents, other study files, and study facilities. BMS audit reports will be kept confidential.

The investigator must notify BMS promptly of any inspections scheduled by regulatory authorities, and promptly forward copies of inspection reports to BMS.

### **9.1.2.1    *Source Documentation***

The Investigator is responsible for ensuring that the source data are accurate, legible, contemporaneous, original and attributable, whether the data are hand-written on paper or entered electronically. If source data are created (first entered), modified, maintained, archived, retrieved, or transmitted electronically via computerized systems (and/or any other kind of electronic devices) as part of regulated clinical trial activities, such systems must be compliant with all applicable laws and regulations governing use of electronic records and/or electronic signatures. Such systems may include, but are not limited to, electronic medical/health records (EMRs/EHRs), adverse event tracking/reporting, protocol required assessments, and/or drug accountability records).

When paper records from such systems are used in place of electronic format to perform regulated activities, such paper records should be certified copies. A certified copy consists of a copy of original information that has been verified, as indicated by a dated signature, as an exact copy having all of the same attributes and information as the original.

### **9.1.3    *Investigational Site Training***

Bristol-Myers Squibb will provide quality investigational staff training prior to study initiation. Training topics will include but are not limited to: GCP, AE reporting, study details and procedure, electronic CRFs, study documentation, informed consent, and enrollment of WOCBP.

## **9.2        *Records***

### **9.2.1    *Records Retention***

The investigator must retain all study records and source documents for the maximum period required by applicable regulations and guidelines, or institution procedures, or for the period specified by BMS, whichever is longer. The investigator must contact BMS prior to destroying any records associated with the study.

BMS will notify the investigator when the study records are no longer needed.

If the investigator withdraws from the study (eg, relocation, retirement), the records shall be transferred to a mutually agreed upon designee (eg, another investigator, IRB). Notice of such transfer will be given in writing to BMS.

### **9.2.2    *Study Drug Records***

It is the responsibility of the investigator to ensure that a current disposition record of study drug (inventoried and dispensed) is maintained at the study site to include investigational product. Records or logs must comply with applicable regulations and guidelines and should include:

- amount received and placed in storage area
- amount currently in storage area
- label identification number or batch number
- amount dispensed to and returned by each subject, including unique subject identifiers

- amount transferred to another area/site for dispensing or storage
- nonstudy disposition (eg, lost, wasted)
- amount destroyed at study site, if applicable
- amount returned to BMS
- retain samples for bioavailability/bioequivalence, if applicable
- dates and initials of person responsible for Investigational Product dispensing/accountability, as per the Delegation of Authority Form

BMS will provide forms to facilitate inventory control if the investigational site does not have an established system that meets these requirements.

### **9.2.3 Case Report Forms**

An investigator is required to prepare and maintain adequate and accurate case histories designed to record all observations and other data pertinent to the investigation on each individual treated or entered as a control in the investigation. Data that are derived from source documents and reported on the CRF must be consistent with the source documents or the discrepancies must be explained. Additional clinical information may be collected and analyzed in an effort to enhance understanding of product safety. CRFs may be requested for AEs and/or laboratory abnormalities that are reported or identified during the course of the study.

For sites using the BMS electronic data capture tool, electronic CRFs will be prepared for all data collection fields except for fields specific to SAEs and pregnancy, which will be reported on the paper or electronic SAE form and Pregnancy Surveillance form, respectively. Spaces may be left blank only in those circumstances permitted by study-specific CRF completion guidelines provided by BMS.

The confidentiality of records that could identify subjects must be protected, respecting the privacy and confidentiality rules in accordance with the applicable regulatory requirement(s).

The investigator will maintain a signature sheet to document signatures and initials of all persons authorized to make entries and/or corrections on CRFs.

The completed CRF, including any paper or electronic SAE/pregnancy CRFs, must be promptly reviewed, signed, and dated by the investigator or qualified physician who is a subinvestigator and who is delegated this task on the Delegation of Authority Form. For electronic CRFs, review and approval/signature is completed electronically through the BMS electronic data capture tool. The investigator must retain a copy of the CRFs including records of the changes and corrections.

Each individual electronically signing electronic CRFs must meet BMS training requirements and must only access the BMS electronic data capture tool using the unique user account provided by BMS. User accounts are not to be shared or reassigned to other individuals.

### **9.3 Clinical Study Report and Publications**

A Signatory Investigator must be selected to sign the clinical study report.

For this protocol, the Signatory Investigator will be selected as appropriate based on the following criteria:

- External Principal Investigator designated at protocol development
- National Coordinating Investigator
- Study Steering Committee chair or their designee
- Subject recruitment (eg, among the top quartile of enrollers)
- Involvement in trial design
- Regional representation (eg, among top quartile of enrollers from a specified region or country)
- Other criteria (as determined by the study team)

The data collected during this study are confidential and proprietary to BMS. Any publications or abstracts arising from this study must adhere to the publication requirements set forth in the clinical trial agreement (CTA) governing [Study site or Investigator] participation in the study. These requirements include, but are not limited to, submitting proposed publications to BMS at the earliest practicable time prior to submission or presentation and otherwise within the time period set forth in the CTA.

## 10 GLOSSARY OF TERMS

Term	Definition
Complete Abstinence	
If one form of contraception is required, Complete Abstinence is defined as complete avoidance of heterosexual intercourse and is an acceptable form of contraception for all study drugs. Female subjects must continue to have pregnancy tests. Acceptable alternate methods of highly effective contraception must be discussed in the event that the subject chooses to forego complete abstinence.
 
If two forms of contraception is required, Complete abstinence is defined as complete avoidance of heterosexual intercourse and is an acceptable form of contraception for all study drugs. Subjects who choose complete abstinence are not required to use a second method of contraception, but female subjects must continue to have pregnancy tests. Acceptable alternate methods of highly effective contraception must be discussed in the event that the subject chooses to forego complete abstinence.
 
Expanded definition Complete abstinence as defined as complete avoidance of heterosexual intercourse is an acceptable form of contraception for all study drugs. This also means that abstinence is the preferred and usual lifestyle of the patient. This does not mean periodic abstinence (eg, calendar, ovulation, symptothermal, profession of abstinence for entry into a clinical trial, post-ovulation methods) and withdrawal, which are not acceptable methods of contraception. Subjects who choose complete abstinence are not required to use a second method of contraception, but female subjects must continue to have pregnancy tests. Acceptable alternate methods of highly effective contraception must be discussed in the event that the subject chooses to forego complete abstinence.

## 11 LIST OF ABBREVIATIONS

Term	Definition
ABA	abatacept
ACPA	anti-citrullinated protein antibody
ACR	American College of Rheumatology
ADA	adalimumab
AE	adverse event
ALT	alanine aminotransferase
ANA	anti-nuclear antibody
ANC	absolute neutrophil count
anti-CCP	anti-cyclic citrullinated peptide
anti-CCP2	commercially available test for ACPA
AST	aspartate aminotransferase
AT	aminotransaminases
AUC	area under the time-concentration curve
β-HCG	beta-human chorionic gonadotrophin
BMS	Bristol-Myers Squibb
BP	blood pressure
BUN	blood urea nitrogen
C	Celsius
CBC	complete blood count
CFR	Code of Federal Regulations
cm	centimeter
CRF	Case Report Form, paper or electronic
CRP	C-reactive protein
DIP	distal interphalangeal
dL	deciliter
DMARD	disease-modifying anti-rheumatic drug
dsDNA	double-stranded DNA
DSM IV	Diagnostic and Statistical Manual of Mental Disorders (4th Edition)
ECG	electrocardiogram

Term	Definition
eCRF	Electronic Case Report Form
EDC	Electronic Data Capture
eg	exempli gratia (for example)
ENA	extractable nuclear antigen
ESR	Erythrocyte Sedimentation Rate
ET	early termination
EU	European Union
EULAR	European League Against Rheumatism
F	Fahrenheit
FDA	Food and Drug Administration
FSH	follicle stimulating hormone
g	gram
GCP	Good Clinical Practice
GGT	gamma-glutamyl transferase
h	hour
HBcAb	Hepatitis B core antibody
HBsAg	hepatitis B surface antigen
HBV	hepatitis B virus
HCV	hepatitis C virus
Hgb	hemoglobin
HIV	Human Immunodeficiency Virus
HR	heart rate
HRT	hormone replacement therapy
hsCRP	high-sensitivity C-reactive protein
ICD	International Classification of Diseases
ICH	International Conference on Harmonisation
ie	id est (that is)
IEC	Independent Ethics Committee
IM	intramuscular
IMP	investigational medicinal products

Term	Definition
IND	Investigational New Drug
IP	investigational product
IRB	Institutional Review Board
IU	International Unit
IV	intravenous
kg	kilogram
L	liter
LDH	lactate dehydrogenase
mg	milligram
MHC	major histocompatibility complex
min	minute
mL	milliliter
mmHg	millimeters of mercury
MRHD	maximum recommended human dose
MTD	maximum tolerated dose
MTX	methotrexate
μg	microgram
N	number of subjects or observations
N/A	not applicable
NIMP	non-investigational medicinal products
NP	nurse practitioner
NSAID	nonsteroidal anti-inflammatory drug
NYHA	New York Heart Association
PA	physician assistant
PBMC	Peripheral blood mononuclear cell
PGA	Physicians Global Assessment of Disease Activity
PO	per os (by mouth route of administration)
PT	prothrombin time
QC	quality control
QD, qd	quaque die, once daily

Term	Definition
RA	rheumatoid arthritis
RBC	red blood cell
RF	Rheumatoid factor
SAE	serious adverse event
SC	subcutaneous
SD	standard deviation
SLE	systemic lupus erythematosus
SOP	Standard Operating Procedures
Subj	subject
t	temperature
T	time
TAO	Trial Access Online, the BMS implementation of an EDC capability
TB	tuberculosis
TNF	tumor necrosis factor
WBC	white blood cell
US	United States
WHO	World Health Organization
WOCBP	women of childbearing potential

2 STUDY DESCRIPTION

2.1 Study Design

This is an exploratory, randomized, single-blinded assessment study in subjects with early RA defined as symptoms of RA for no more than 12 months prior to screening and satisfying the criteria for RA according to the ACR/EULAR 2010 classification at some point during the 12-month period. Eligible subjects must have been on methotrexate (MTX) for at least 12 weeks with a stable dose of MTX for at least 28 days prior to randomization and are naive to biologic DMARD. The study consists of a screening period of up to 28 days, followed by a 24-week single-blind treatment period with abatacept or adalimumab, followed by a 24-week open-label treatment period with abatacept, followed by an 85-day follow-up period.

Eligibility will be based on specified inclusion and exclusion criteria, medical history, disease activity and safety assessments. Randomization must occur within 28 days of signing the informed consent.

On Day 1, subjects will be randomized to one of two parallel treatment arms in a 1:1 ratio:

- abatacept SC (125mg) weekly
- adalimumab SC (40mg) once every two weeks

All subjects continuing in the open-label treatment period will receive abatacept 125mg SC, weekly. Those subjects randomized to adalimumab will switch to abatacept at Week 28 following a six week washout period. The dose of methotrexate must remain stable throughout the study and may only be lowered due to intolerance or adverse event. Subjects not wishing to continue on open-label abatacept have the option of discontinuing treatment at the end of the single-blind period and proceeding to the post-treatment follow-up period.

Subjects who discontinue treatment of study drug or complete the study will have one follow-up visit 85 days after the last dose of investigational product to perform safety assessments.

2.2 Treatment Assignment

At the time of enrollment, immediately after written informed consent is obtained and before any study-related procedures are performed, each subject will be assigned a unique, sequential five-digit number beginning with 00001, 00002, 00003 and so on, for identification throughout the study. This study number must not be reused for any other subject. The study physician or research coordinator must contact the Central Randomization System to enroll each subject into a centralized database at the time consent is obtained.

After completion of all screening evaluations and concomitant medication adjustment or stabilization, all eligible subjects will be randomized into the single-blind treatment phase of the study. Randomization schedules will be generated and kept by the Randomization Group within Drug Supply Management of Bristol-Myers Squibb. Each subject who qualifies for treatment will be assigned a unique randomization number. Randomization numbers will be assigned using a Central Randomization System in the order in which subjects qualify for treatment, not in the order of study enrollment. Subjects will be randomized on a 1:1 basis to either the abatacept treatment arm or the adalimumab treatment arm.

2.3 Blinding and Unblinding

Double blinding of study drug, adalimumab vis-à-vis abatacept, is not feasible due to logistical barriers around re-packaging adalimumab as well as the expected differences in injection site reactions. Both of these together make effective blinding of the patients to the randomized drug assignment impractical and unsustainable. The nature and frequency of adalimumab-associated injection site reactions makes blinding investigators responsible for clinical care unsustainable under usual practices. It is possible, however, to preserve the objectivity of clinical assessments with the following strategy that has been designed to establish and maintain a single-blinded assessor for clinical endpoints throughout the study. This will require a minimum of 3 individuals: a blinded clinical assessor, an unblinded Study Research Coordinator and an unblinded physician investigator/subinvestigator to complete/approve the CRF.

2.4 Protocol Amendments

The purpose of Amendment 1 (March 14, 2016) is to extend the treatment period of the study an additional 24 weeks. Subjects receiving abatacept will continue to receive abatacept for the additional 24 weeks. Subjects receiving adalimumab will switch to abatacept at Week 28 following a six week washout period and continue treatment with abatacept for the additional 24 weeks.

The purpose of Amendment 2 (June 8, 2016) is to modify some of the inclusion criteria to better align the characteristics of the targeted study population with patients with early Rheumatoid Arthritis seen in clinical practice.

The purpose of Amendment 6 (February 22, 2017) is to include the addition of blood sample collection for PBMC.

3 OBJECTIVES

3.1 Primary

Not applicable

[figure not shown]
3.2 Secondary

Not applicable

4 ENDPOINTS

No primary or secondary endpoints are defined for this protocol.

5 SAMPLE SIZE AND POWER

In this study, 25 subjects will be randomized per treatment arm.

This is an exploratory study with only exploratory objectives. No formal sample size and power calculation was provided. It should be noted that with 25 subjects per arm the half width of the 95% CI for differences in proportion (e.g., proportion of seroconversion for anti-CCP2, ACPA) will range from 25 to 30%. This means that only if the treatment difference in proportion is larger than 25-30% the difference will be declared statistically significant at 5% significance level. For changes from baseline in continuous variables the minimum detectable effect size (treatment difference in changes divided by common standard deviation) to declare statistical significance (with 5% significance level) is 0.57.

During the study, the sample size was increased to get at least 30 subjects with additional collection of blood for With 40 (instead of 25) subjects per arm the half width of the 95% CI for differences in proportion (e.g., proportion of seroconversion for anti-CCP2, ACPA) will range from 17% to 21%. This means that only if the treatment difference in proportion is larger than 17-21% the difference will be declared statistically significant at 5% significance level. For changes from baseline in continuous variables the minimum detectable effect size (treatment difference in changes divided by common standard deviation) to declare statistical significance (with 5% significance level) is 0.44.

6 STUDY PERIODS, TREATMENT REGIMENS AND POPULATIONS FOR ANALYSES

6.1 Study Periods

The following periods are defined for this statistical analysis plan:

- The pre-treatment period covers the time period prior to or on the first dose time of single-blind study medication.
- The single-blind treatment period starts at the time of the first dose of single-blind study medication and lasts until :
 - the time of the last dose of single-blind study medication for concomitant medication summaries
 - 56 days post last dose of single-blind study medication for subjects who do not enter OL. For those subjects who do enter OL, the single-blind treatment period lasts until first day of open-label for abatacept randomized subjects or until 10 days post last dose of single-blind treatment for adalimumab randomized subjects for safety analyses (AE and labs).
 - 21 days post last dose of single-blind study medication for subjects who do not enter OL For those subject who do enter OL, the single-blind treatment period lasts until first day of open-label for abatacept randomized subjects or until 10 days post last dose of single-blind treatment for adalimumab randomized subjects for immunogenicity analyses

Note: To align the cut-off of the single-blind treatment period for abatacept and adalimumab and taking into account that for adalimumab there is a wash-out period of 6 weeks, 10 days is

used to cut the single-blind treatment period for adalimumab. Ten (10) is equal to the expected maximum number of days after last single-blind abatacept dose and prior to first open-label abatacept dose (7 days +/- 3 days).

- The open-label abatacept treatment period starts at the time of the first dose of open-label abatacept treatment and lasts until 56 days post last open-label abatacept dose (AE and labs), except for immunogenicity analyses for which the open-label period goes up to 21 days post last open-label abatacept dose.
- The cumulative abatacept period starts at the time of the first dose of abatacept (single-blind or open-label) and lasts until 56 days post last abatacept dose (single-blind or open-label), except for immunogenicity analyses for which the cumulative abatacept period goes up to 21 days post last abatacept dose.

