7.7.1 Adverse Events

All AEs are coded and grouped into Preferred Terms (PT) by System Organ Class (SOC), using the latest approved version of the Medical Dictionary for Regulatory Activities (MedDRA) at the time of database lock. Listings and summaries will be based on the resulting SOCs and PTs.

All reported AEs during the single-blind treatment period and all reported AEs reported during the cumulative abatacept period will be listed, indicating the subjects id, age, gender, the date of onset, the day of onset relative to the start of treatment, investigator's assessment of severity and relationship to study drug.

In addition, all reported AEs during the washout-out period (beyond 20 days past last single blind dose of adalimumab up to first dose of open-label abatacept) will be in a separate listing. This listing will only include adalimumab patients who are treated with OL abatacept. The threshold of 20 days is chosen for this listing, because AEs up to 20 days past last single-blind dose of adalimumab are included in the AE summaries of the single-blind period. It should be noted that for the single-blind analysis a threshold of 20 days (post-hoc) was used instead of 10 days defined in version 1.0 of SAP.

AEs will be summarized for the single-blind treatment period and the cumulative abatacept period. This period is defined in [Section 6.1](#). These AE summaries will be based on proportions, which represent the number of subjects experiencing the AEs divided by the number of subjects who received at least 1 dose of single-blind study medication for the Week 24 analysis and by the number of subjects treated with abatacept for the cumulative abatacept period analysis.

Any AEs irrespectively of when they occur, but will appear on the above mentioned comprehensive listing.

Summary information (the number and percent of subjects by treatment) will be tabulated for the following AEs:

- all AEs including clinical and laboratory AEs
 - most common AEs (reported in 10% of subjects or more in any treatment group)
 - categorized by severity
- related events
 - most common (reported in 5% of subjects or more in any treatment group)
 - categorized by severity
- serious adverse events (SAEs)
- discontinuations due to SAEs/AEs

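### The single-blind safety window depends on later open-label entry: an adalimumab washout event that stops the switch is tabulated, while the same event in a switcher is only listed

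*SAP*

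**What the plan says.** SAP 6.1 sets the end of the single-blind period for adverse events (AEs) and laboratory data by what the subject does next:

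- Subjects who do not enter open label (OL), in either arm: "56 days post last dose of single-blind study medication for subjects who do not enter OL".
- Abatacept subjects who enter OL: "the single-blind treatment period lasts until first day of open-label for abatacept randomized subjects".
- Adalimumab subjects who enter OL: "until 10 days post last dose of single-blind treatment for adalimumab randomized subjects for safety analyses (AE and labs".

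The stated purpose is to align the arms: "Ten (10) is equal to the expected maximum number of days after last single-blind abatacept dose and prior to first open-label abatacept dose".

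SAP 2.1 gives the adalimumab timing: "Those subjects randomized to adalimumab will switch to abatacept at Week 28 following a six week washout period".

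SAP 7.7.1 then reports that "for the single-blind analysis a threshold of 20 days (post-hoc) was used instead of 10 days defined in version 1.0 of SAP". It adds that "AEs up to 20 days past last single-blind dose of adalimumab are included in the AE summaries of the single-blind period", and sends later washout events to a separate listing: "This listing will only include adalimumab patients who are treated with OL abatacept". AE proportions are divided by all subjects who received at least one single-blind dose. SAP 7.7 excludes statistical testing of AE frequencies between groups.

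**The concern.** The length of follow-up counted in the between-arm safety tables is decided by something that happens after the last single-blind dose. For abatacept this matters little, because entry follows within about a week. For adalimumab, six weeks pass before entry is settled, and an event in those weeks can itself prevent entry.

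Take two adalimumab subjects with the same event 30 days after the last dose. One switches as planned, so the event falls after the single-blind cut. It also falls before the cumulative abatacept period, which SAP 6.1 starts at the first abatacept dose, so no summary contains it. The other does not switch because of the event. That subject's window becomes 56 days, and the event enters the single-blind adalimumab tables. A death is the clearest case: a subject who dies in the washout cannot enter OL, so the death always counts as single-blind adalimumab. A continuing abatacept subject who dies 30 days after the last single-blind dose is already in OL and is outside the single-blind listing.

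At stake are the by-arm tables of AEs, serious AEs, infections and deaths. They are the trial's only randomised safety comparison.

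**Working it through.** **The plan's own figures.** The 10-day cut is 7 + 3 = 10. The 56-day offset is described in SAP 7.4.1 as about four half-lives; Protocol 3.3.1 gives five half-lives as 70 days, so 4 x 70/5 = 56. Both reproduce.

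**Length of the gap.** Dosing every 14 days from Day 1 puts the Week 22 adalimumab dose on Day 1 + 11 x 14 = 155. Week 28 is Day 197 (SAP 8.5). 197 - 155 = 42 days, which matches the six weeks in SAP 2.1. (Protocol 4.5.2 prints Day 152 for Week 22, which would give 45; I use the SAP's 42.) For abatacept, the Week 23 dose is on Day 162 and Week 24 is Day 169: a gap of 7 days, at most 10.

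**Days counted after the last single-blind dose.**

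| | Enters OL | Does not enter OL | Days on which entry is still open and counting depends on it |
|---|---|---|---|
| Abatacept | about 7-10 | 56 | almost none |
| Adalimumab, 10-day cut | 10 | 56 | 11-42 (32 days) |
| Adalimumab, 20-day cut | 20 | 56 | 21-42 (22 days) |

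**What the rule does when the drugs do not differ.** Let both arms have the same constant AE rate r, with F(d) = 1 - exp(-r x d/365.25). Let e be the proportion otherwise set to enter OL, and q the chance that an event between the cut and day 42 stops the switch. The proportion with a tabulated event after the last dose is:

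- adalimumab: e x [F(cut) + q x (F(42) - F(cut))] + (1 - e) x F(56)
- abatacept: e x F(gap) + (1 - e) x F(56)

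The documents give none of r, e and q. I assume r = 1-3 per patient-year, e = 80-90% and q = 0-50%. At r = 2: F(10) = 5.3%, F(20) = 10.4%, F(42) = 20.5%, F(56) = 26.4%.

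With e = 80%, a 10-day cut and an abatacept gap of 10 days:

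- q = 0: each arm 0.8 x 5.3 + 0.2 x 26.4 = 9.5%; difference 0.0 points.
- q = 10%, 25%, 50%: adalimumab higher by 0.8 x q x (20.5 - 5.3) = 1.2, 3.0, 6.1 points.
- At q = 0, 0.8 x (20.5 - 5.3) = about 12% of adalimumab subjects (4.9 of 40) have a first post-dose event that no summary shows.
- Entry of 80% on adalimumab and 90% on abatacept, q = 0: +0.1 x (26.4 - 5.3) = +2.1 points; reversed, -2.1.
- 20-day cut, q = 0, equal entry: +0.8 x (10.4 - 5.3) = about +4.0 points, because abatacept entrants still stop by day 10. This comes from the mismatch of cuts, not from event-driven switching.

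Over the full assumed ranges with q = 10-50%, the 10-day cut gives +0.7 to +9.6 points.

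**Allowing for subjects already counted.** The tables count subjects, not events. At r = 2, the chance of no AE from Day 1 to Day 155 is exp(-2 x 154/365.25) = 43%. In the any-AE row, 1.2-6.1 points therefore shrink to about 0.5-2.6. In rare rows (serious AEs, deaths) few subjects are already counted, and one new subject is 1/40 = 2.5 points (1/25 = 4 points at the initial sample size).

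**How often in a rare row.** With an assumed 36 prospective switchers, the 22-day interval holds 36 x 22/365.25 = 2.17 patient-years. One expected serious AE needs a rate of about 0.46 per patient-year; three need about 1.4.

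**The same model under one cut.** Counting every subject to 10 days gives 2.7%, 5.3% and 7.9% in both arms at r = 1, 2 and 3: no arm difference for any e or q.

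**The case against.** - *Switchers' washout is partly tabulated and otherwise disclosed.* A reader might infer that washout events are tabulated only for those who fail to switch. That is too strong. Switchers' first 10 days (SAP 6.1) or 20 days (SAP 7.7.1) are in the summaries, and later events are listed.
- *The 56-day rule covers both arms.* An abatacept subject who stops early or declines OL is also followed to day 56. This stands, so the arms differ only in the interval during which entry remains open.
- *The entry rules are not in the documents.* The protocol supplied predates the OL period. Its dosing sections describe interruption with resumption after full resolution, which could mean a delayed rather than an abandoned switch. SAP 2.1 places the voluntary opt-out at the end of the single-blind period, about 14 days after the Week 22 dose, so most elective non-entry is settled early in the washout. This stands as a limit on frequency. It does not remove the mechanism, since a death needs no entry rule.
- *The comparison is exploratory and untested.* No error rate is affected. But 6.1 states that the cut exists to align the arms, and making it depend on entry works against that aim.

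**Conclusion.** The structural point holds. The single-blind safety window is conditioned on a later event, and only the adalimumab arm has a long interval (32 days, or 22 under the 20-day cut) in which an event can decide whether it is itself counted.

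A reader might infer that the tables are necessarily tilted against adalimumab. The documents do not support that. The bias runs against adalimumab if events stop the switch, and in either direction if OL entry rates differ. It is about zero under the 10-day cut if entry is equal and unrelated to events. A reader might also multiply 2.5 or 4 points by some number of affected subjects; the documents give no such number, and a subject already counted in a row adds nothing to it. The modelled 0.7 to 9.6 points rest on assumed r, e and q, and overstate common rows. What is firm is the rule, the day counts, and that one subject newly counted in a row is 2.5 points at 40 per arm. That matters for serious AEs and deaths.

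**What to change.** 1. For the between-arm single-blind safety tables, end the period for every treated subject 10 days after the last single-blind dose, or at first OL dose if earlier, whatever the later OL entry. Ten days is the SAP's own alignment figure. A residual remains: an abatacept subject who enters on the 7-day target day loses up to 3 days. If all did so, the null model leaves 1.3 points at r = 2 and e = 80%, before allowing for subjects already counted.
2. Add a post-single-blind/washout table by randomised arm covering all subjects, from that cut to the earlier of 56 days after the last single-blind dose or first OL dose. Remove the restriction of the washout listing to subjects treated with OL abatacept.
3. Reconcile the 10 days in SAP 6.1, 7.4.1 and 8.5 with the 20 days in 7.7.1, and say whether the 20 days also applied to laboratory data.
4. Match exposure to the new window. SAP 7.4.1 gives +56 days for subjects not treated in OL, but its +10 formula for adalimumab is not limited to OL entrants, so adalimumab non-entrants fall under both. The exposure-adjusted rates in 7.7.6 need the same window in numerator and denominator.

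Cost: SAP wording, the exposure derivation and one table, with no new data. Late events in non-entrants move from the main table to the second one. If the first lock has passed, present both tables as supplementary.
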